6.1.4. Electrocardiograms

If more than one ECG is collected at a nominal time post-dose (for example, triplicate ECGs), the mean of the replicate measurements will be used to represent a single observation at that time point.

Absolute values and changes from baseline in QT, heart rate, QTcF, PR, RR and QRS will be summarized by dose cohort, ambulatory status at baseline, and study visit. Tables will be paged by parameter. Baseline is as defined in Section 3.1.4.

The maximum absolute value (post-dose) and the maximum increase from baseline for QT, heart rate, QTcF, PR, and QRS will be determined over all measurements taken post-dose.

The maximum increase from baseline will be calculated by first subtracting the baseline value from each post-dose measurement to give the change from baseline. The maximum of these values over the respective period will then be selected, except in the case where a participant does not show an increase. In such an instance, the minimum decrease should be taken.

Maximum increase from baseline for QT, heart rate, QTcF, PR and QRS will be summarized by dose cohort and ambulatory status.

ECG endpoints and changes from baseline (QTcF, PR and QRS) will also be summarized descriptively by dose cohort and ambulatory status at baseline using categories as defined in Appendix 1 (for QTc these correspond to ICH E14⁸). Numbers and percentages of participants meeting the categorical criteria will be provided. All planned and unplanned measurements will be counted in these categorical summaries. All values meeting the criteria of potential clinical concern will be listed.

For triplicate ECGs, if any of the three individual ECG tracings has a QTcF value \geq 500 msec, but the mean of the triplicates is not \geq 500 msec, the data from the participant's individual tracing will be described in a safety section of the CSR in order to place the \geq 500 msec value in appropriate clinical context. However, values from individual tracings within triplicate measurements that are \geq 500 msec will not be included in the categorical analysis

unless the average from the triplicate measurements is also ≥500 msec. Changes from baseline will be defined as the change between QTcF post-dose from the average of the last pre-dose triplicate values on the dosing day in each period.

6.1.5. Physical Examination and Neurological Examinations

Abnormal and clinically relevant changes in physical and neurological in AE tables by dose cohort and ambulatory status at baseline.

6.1.6. Cardiac MRI (or Echocardiogram, if necessary)

Cardiac MRI results including the LVEF, left arterial diameter, LV mass index, LV end-diastolic diameter, LV end-systolic diameter, fractional shortening, LV wall thickness, LV posterior wall thickness, tricuspid valvular regurgitation presence and pericardial effusion will be provided in a data listing. Changes from baseline in the following parameters will be summarized descriptively by dose cohort and ambulatory status at baseline:

- LVEF (%)
- LV Fractional Shortening (%)
- LV mass index
- Presence or absence of late gadolinium enhancement
- Observations from the cardiac MRI will be used for reporting. If cardiac MRI was not conducted at the scheduled visit (eg, due to young subject's inability to remain still during the scan), the results from the echocardiogram (if available for at least 3 participants with baseline assessments in the same dose cohort) will be summarized and listed separately.

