2. STUDY OBJECTIVES AND ENDPOINTS

Primary Objective:	Primary Endpoints:
To determine the safety and tolerability of a single IV infusion of PF-06939926 in subjects with DMD at ascending doses.	 Incidence of both dose-limiting and treatment-related adverse events (AEs), inclusive of infusion and injection site reactions, through 1 year post-treatment. Incidence, severity, and causal relationship of treatment-emergent AEs (TEAEs) through 1 year post-treatment. Incidence and magnitude of abnormal laboratory findings through 1 year post-treatment. Abnormal and clinically relevant changes in physical and neurological examinations, weight, vital signs, electrocardiogram (ECG), cardiac magnetic resonance imaging (MRI)- (or echocardiogram-) measured left ventricular ejection fraction (LVEF), Columbia Suicide Severity Rating Scale (C-SSRS) through 1 year post-treatment.
• Secondary Objectives:	Secondary Endpoints:
 To determine the amount and distribution of mini-dystrophin expression in the muscle of subjects with DMD following a single IV infusion of PF-06939926 at ascending doses. To evaluate long term safety of a single IV infusion of PF-06939926 in subjects with DMD at ascending doses. 	 Evidence of mini-dystrophin expression and transduction in muscle by immunohistochemistry (IHC) and Western Blot (WB) and/or LC-MS using muscle biopsies at 2 or 3 and 6 or 12 months post-treatment. Incidence, severity and causal relationship of TEAEs and clinically significant safety findings, as described for the

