7.2.7.2. Cardiac MRI (or Echocardiogram, if necessary)

Cardiac MRI should be collected at times specified in the Schedule of Activities section of this protocol.

Cardiac MRI with gadolinium is the preferred method for cardiac imaging, when possible. When cardiac MRI with gadolinium is used, it should only be collected after thigh and upper limb MRI is complete. Otherwise cardiac MRI should be done on a different visit day from the thigh and upper limb MRI. If the subject has a contraindication to gadolinium, cardiac MRI without gadolinium will be acceptable. Cardiac MRI will be read by a central imaging vendor and only the results of the LVEF will be provided to sites.

FOR AMBULATORY SUBJECTS: If the LVEF falls below 50% on the cardiac MRI at any follow-up visit, the subject should be referred to a cardiologist for further assessment.

FOR NON-AMBULATORY SUBJECTS: For those non-ambulatory subjects for whom the LVEF is already <50% at Screening, documentation of consultation with a cardiologist at least annually should be kept on file as part of standard of care.

Sites will be provided with a scanning and image transmittal guide for collection of the cardiac MRI.

If the cardiac MRI is deemed unable to be evaluated and a repeat MRI is unlikely to resolve the issue (eg, if subject is unable to remain still in the scanner), a locally-read echocardiogram may be an acceptable substitute. To ensure safety of the subjects, a qualified individual at the site will evaluate the echocardiogram at least for LVEF, but other parameters may also be assessed, such as ventricular systolic pressure, left arterial diameter,

left ventricular mass index, left ventricular end diastolic diameter, left ventricular end systolic diameter, shortening fraction, left ventricular posterior wall thickness, tricuspid valvular regurgitation presence and pericardial effusion.

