9.2. Safety Analysis

Adverse events, ECGs, vital signs (blood pressure and heart rate), physical & neurological examinations, cardiac MRI (or echocardiogram) and safety laboratory data (including hematology, chemistry and urinalysis) will be reviewed and summarized on an ongoing basis during the study to evaluate the safety of subjects. Safety data will be presented in tabular and/or graphical format and summarized descriptively, where appropriate. Incidence and severity of TEAEs, withdrawals due to TEAEs, and infusion and injection site reactions will be summarized by dose level and ambulatory status at baseline. Abnormal and clinically relevant changes in physical and neurological examinations, height and weight, vital signs, cardiac MRI (or echocardiogram) and ECG parameters will be summarized by dose level, ambulatory status at baseline, and study day. Incidence and magnitude of abnormal laboratory findings will be summarized by dose level and ambulatory status at baseline.

Medical history and medication history, as applicable, collected during the course of the study will be captured for inclusion into the study database, unless otherwise noted. Any untoward findings identified on physical examination conducted after the administration of the investigational product will be captured as an adverse event, if those findings meet the definition of an adverse event. Data collected at Screening that are used for inclusion/exclusion criteria, such as laboratory data, ECGs and vital signs will be included in the study database. Demographic data collected at Screening will be reported.

Primary safety analyses will be based on the data through 1-year post treatment. Secondary safety analyses will be based on the long-term follow up data through 5-years post treatment.

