3. ENDPOINTS AND BASELINE VARIABLES: DEFINITIONS

3.1. Primary Endpoints

- Incidence of both dose-limiting and treatment-related AEs, inclusive of infusion and injection site reactions, through 1 year post-treatment.
- *Incidence, severity, and causal relationship of TEAEs through 1 year posttreatment.*
- Incidence and magnitude of abnormal laboratory findings through 1 year posttreatment.
- Abnormal and clinically relevant changes in physical and neurological examinations, weight, vital signs, ECG, cardiac MRI (or echocardiogram-) measured LVEF, CSSRS through 1 year posttreatment.

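### SAP 6.1.6 applies its 3-participant minimum to the listing of echocardiogram results as well as the summary, so one or two participants' LVEF in a dose cohort can be left out of the LVEF outputs

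*SAP*

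**What the plan says.** Protocol Section 2 makes LVEF a primary safety endpoint through one year and accepts either modality ("or echocardiogram-) measured left ventricular ejection fraction (LVEF"). SAP 3.1 repeats this ("cardiac MRI (or echocardiogram-) measured LVEF, CSSRS through 1 year posttreatment"). Protocol 7.2.7.2 explains why both are needed: where an MRI cannot be evaluated and a repeat is unlikely to help, "a locally-read echocardiogram may be an acceptable substitute".

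SAP 6.1.6 then sets the reporting rules:

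- The default source is MRI: "Observations from the cardiac MRI will be used for reporting".
- A data listing with no minimum count is promised, but its wording is confined to MRI: "Cardiac MRI results including the LVEF, left arterial diameter, LV mass index" and further parameters.
- Where MRI was not conducted at the visit, echocardiogram results, "if available for at least 3 participants with baseline assessments in the same dose cohort) will be summarized and listed separately".

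Two broader statements set no minimum. The opening of SAP 6.1 provides both a listing and a summary for the Section 3.1 endpoints. Protocol 9.2 says that changes in "cardiac MRI (or echocardiogram) and ECG parameters will be summarized by dose level, ambulatory status at baseline, and study day".

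**The concern.** A minimum of 3 is sensible for a mean or standard deviation. It has no purpose for a listing, which shows individual values and needs no group size. As punctuated, the condition in 6.1.6 attaches to both verbs, so a programmer following the specific text would produce no echocardiogram listing for a dose cohort with one or two such participants.

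What is at stake is the completeness of a primary safety endpoint in a first-in-human study of 22 participants, where individual values carry most of the information. The Schedule of Activities has cardiac imaging at Screening, at Week 52 and then annually. A participant who has an echocardiogram instead of an MRI at Week 52 could therefore have no post-dose LVEF in the one-year output at all. Nor is the reason for substitution obviously unrelated to the participant's condition: 6.1.6 gives young age as its example, and Protocol Section 7 links MRI intolerance to loss of ambulation.

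**Working it through.** The plan states no figure for this rule, so there is nothing to reproduce. The check compares the texts and then bounds the effect.

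**Texts side by side**

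| Source | Listing of echocardiogram LVEF | Summary | Minimum count |
|---|---|---|---|
| Protocol 9.2 | not addressed | yes | none |
| SAP 6.1, opening rule | yes | yes | none |
| SAP 6.1.6, MRI listing | MRI named; echocardiogram not named | not applicable | none |
| SAP 6.1.6, echocardiogram sentence | conditional | conditional | 3 per dose cohort, with baseline |

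The last row is the only one with a minimum, and it is the most specific.

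**Inputs.** SAP 2.5 gives 3 ambulatory low-dose, 16 ambulatory high-dose and 3 non-ambulatory high-dose participants: 3 + 16 + 3 = 22. SAP Section 4 defines the high dose cohort by dose alone, so it has 16 + 3 = 19 participants. The low dose cohort has 3.

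**Upper bound.** The largest count below 3 is 2. Applying the rule per dose cohort and visit:

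- low dose: 2/3 = 66.7%
- high dose: 2/19 = 10.5%
- overall: (2 + 2)/22 = 4/22 = 18.2%

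In the low dose cohort, all 3 participants must have an echocardiogram before any such result appears.

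**Illustration under an assumed rate.** The documents do not say how often echocardiogram replaces MRI. Let q be the assumed probability that a participant has an echocardiogram instead of an MRI at a visit, independently of the others, and let X be the number in a cohort of n. Results exist but are left out when X is 1 or 2:

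P(X = 1 or 2) = n q (1 − q)^(n−1) + [n(n − 1)/2] q² (1 − q)^(n−2)

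For n = 3 and q = 0.10: 3(0.10)(0.81) + 3(0.01)(0.90) = 0.243 + 0.027 = 0.27.

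| Assumed q | Low dose, n = 3 | High dose, n = 19 |
|---|---|---|
| 0.05 | 0.14 | 0.56 |
| 0.10 | 0.27 | 0.57 |
| 0.20 | 0.48 | 0.22 |
| 0.30 | 0.63 | 0.05 |

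Across this range the chance that the rule takes effect runs from 0.14 to 0.63 at low dose and from 0.05 to 0.57 at high dose. At high dose it falls as q rises, because the threshold of 3 is then usually met.

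**Two further gaps in the same sentence**

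1. The trigger in 6.1.6 is an MRI not conducted. The protocol also allows echocardiogram after an MRI that was attempted but could not be evaluated. The SAP's own example, a child unable to keep still, suggests that this case is intended, but the wording does not clearly cover it.
2. The participants counted must have baseline assessments, but the modality of that baseline is not stated. SAP 3.1.5 defines baseline only as the last pre-dose measurement. A participant with MRI at baseline and echocardiogram later may or may not count toward the 3.

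**The case against.** The strongest reply is that the results are covered elsewhere in the plan.

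- **The general rule.** SAP 6.1 already promises a listing of this endpoint. That stands, and it makes this an inconsistency within the SAP rather than a settled plan to omit results. It does not remove the problem, because the specific sentence in 6.1.6 contradicts it.
- **The MRI listing may be meant to include echocardiogram.** It sits under a heading naming both modalities, and its parameters closely follow those that Protocol 7.2.7.2 gives for echocardiogram. This is plausible, but the text says MRI results.
- **Small groups may be handled in SAP 5.2.** The version 5 entry in the SAP amendment history describes individual profiles for subgroups of fewer than 3, and the readable text of 5.2 opens with a fragment that could be the end of that sentence. The rule may therefore survive. Whether it reaches participants with echocardiogram only cannot be settled from what is legible, and 6.1.6 does not refer to it.
- **Other routes for a cardiac signal.** Abnormal tests meeting the conditions in Protocol 8.2.2 become adverse events, troponin and ECG are analysed separately, and the E-DMC reviews data as they accrue. All of this stands. What remains exposed is the LVEF value and any fall not recorded as an adverse event.

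A reader might infer that the rule weakens the myocarditis criterion for halting enrolment. It does not. That criterion (Protocol 3.5) turns on a clinical diagnosis and E-DMC review, and SAP 2.5 describes all 22 participants as already dosed. A reader might also infer that the remedy is one table of abnormal LVEF changes counting either modality. The documents do not call for that: MRI is read centrally and echocardiogram locally, and keeping them apart is a defensible choice.

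**Conclusion.** The point holds as a narrow reporting defect. Read literally, SAP 6.1.6 leaves the echocardiogram LVEF of one or two participants per dose cohort per visit out of the LVEF tables and listings, against SAP 6.1 and Protocol 9.2. The ceiling is 2/3 at low dose and 2/19 at high dose.

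This rests on three assumptions: the parenthesis governs both verbs, the count is taken at each visit, and dose cohort has the meaning given in SAP Section 4. If the ambulatory high-dose group alone were meant, the ceiling there would be 2/16 = 12.5%.

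The number actually affected is unknown and could be zero. Tolerating MRI without sedation is an inclusion criterion, which limits substitution at entry. The documents do not support a claim that cardiac signals would disappear or that cardiac safety would look better than it is: they give neither the number of echocardiograms nor the direction of any difference. This is a low-severity point, worth making because the correction costs so little.

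**What to change.** Reword SAP 6.1.6 so that:

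1. every echocardiogram result is listed regardless of count, whether MRI was not conducted or was attempted and could not be evaluated;
2. each listed value is flagged by modality and shown with the participant's baseline value and the modality of that baseline;
3. the 3-participant minimum applies only to echocardiogram summary statistics, which stay separate from MRI, and the sentence states whether the baseline counted toward the 3 must itself be by echocardiogram.

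The cost is a few lines of SAP text and one listing. The data are already collected under the protocol, and neither the endpoint definition nor the MRI analysis changes. With every result listed, no echocardiogram LVEF is left out at any substitution rate.

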6.1.7. Other Safety Data

Changes in weight and the C-SSRS will be summarized by dose cohort and ambulatory status at baseline.

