6.2.3. Long-term safety

To evaluate the long-term safety of the study treatment, analysis of the primary safety endpoints described in Section 6.1 will include all data through 5 years post-treatment. These include the incidence, severity, causal relationship of TEAEs and clinically significant safety findings.

[figure not shown]

[figure not shown]

[figure not shown]

[figure not shown]

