6.5. Baseline and Other Summaries and Analyses

6.5.1. Baseline Summaries

The following data will be summarized by dose cohort, ambulatory status at baseline, and overall.

- 1. Demographic characteristics will be summarized. Age categories to display are:
 - ≥4 to <8 years including subcategories of <5 years, ≥5 to <6 years, ≥6 to <7 years, and ≥7 to <8 years;

- ≥ 8 to ≤ 12 years including subcategories of ≥ 8 to ≤ 9 years, ≥ 9 to ≤ 10 years, ≥ 10 to ≤ 11 years, ≥ 11 to ≤ 12 years;
- >12 to <15 years, ≥ 15 to <18, ≥ 18 to <20 years, ≥ 20 to <25 years, and ≥ 25 years.
- 2. Age at dosing in years
- 3. Age at primary diagnosis in years
- 4. Race and Ethnicity
- 5. Physical measurements (including height, weight, body mass index)
- 6. Dystrophin mutation type
- 7. Background glucocorticoid regimen. Prednisolone and prednisone will be combined for this analysis. The number (%) of participants for each glucocorticoid being received at screening will be presented. Descriptive statistics will be presented for,
- 8. Daily dose (mg/kg) for each glucocorticoid the participant is receiving at screening. This will be calculated from the total daily dose and screening weight collected in the CRF;
- 9. Duration of glucocorticoid use (months) for glucocorticoid dose the participant is receiving at screening; and
- 10. Age at initiation of any glucocorticoid use.
- 11. General medical history
- 12. Prior medications

The following variables will be summarized using descriptive statistics,

- NSAA total score (ambulatory population only);
- Time to rise from floor (ambulatory population only);
- PUL 2.0 total score and each domain;
- %pFVC.

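### The planned summary of raw weight change cannot separate excess or poor gain from expected growth, and the SAP omits the post-baseline height summary set out in Protocol 9.2

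*SAP*

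**What the plan says.** Protocol Section 2 and SAP 3.1 list the same primary safety endpoint. In the SAP it begins "Abnormal and clinically relevant changes in physical and neurological examinations, weight, vital signs, ECG" and runs through 1 year. Weight is on the list and height is not.

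The analysis sections differ. Protocol 9.2 plans to summarise "Abnormal and clinically relevant changes in physical and neurological examinations, height and weight, vital signs" and other safety measures by dose level, baseline ambulatory status and study day. SAP 6.1.7 says that "Changes in weight and the C-SSRS will be summarized by dose cohort and ambulatory status at baseline". It does not mention height, body mass index, any age-adjusted measure or any criterion for an abnormal weight change.

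SAP 6.2.3 carries the same analyses forward: "analysis of the primary safety endpoints described in Section 6.1 will include all data through 5 years post-treatment".

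Elsewhere in the visible SAP, height and body mass index are only baseline variables (Sections 3.4 and 6.5.1). Neither the version history nor the amendment history mentions or explains leaving out post-baseline height. The Protocol's Schedule of Activities has height and weight measured together at Weeks 8, 26 and 52 and at each annual visit.

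**The concern.** Ambulatory participants enter at 4 to 12 years of age (Protocol 4.1), and weight gain is expected in them over 1 year and still more over 5. A gain in kilograms is abnormal only in relation to what a boy of that age and size would be expected to gain. SAP 6.1.7 supplies no such yardstick, and there is no concurrent control group to supply one.

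The risk is not remote. Protocol 1.2.1 names weight gain as a well-known adverse effect of glucocorticoids. Protocol Section 5 raises the daily glucocorticoid dose after infusion, tapers it over about three months and continues daily treatment through at least the first year.

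At stake is whether the report can say that weight change was normal, excessive or deficient. Height bears on the same question, because a given weight gain means one thing in a boy who grew taller and another in a boy who did not. Height would be collected for five years with no visible planned analysis after baseline.

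**Working it through.** **1. Plan against plan.** The documents contain no figure for weight or height change to reproduce, so the first check is textual.

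| Item | Protocol | SAP |
|---|---|---|
| Primary endpoint | Weight (Section 2) | Weight (2.1, 3.1) |
| Post-baseline summary | Height and weight (9.2) | Weight only (6.1.7) |
| Grouping named | Dose level, ambulatory status, study day | Dose cohort, ambulatory status |
| Criterion for abnormal weight change | None | None |

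The SAP does set criteria for other safety measures: ECG categories in Appendix 1, multiples of baseline or of the upper limit of normal for cardiac troponin I in 6.1.2, and abnormality criteria for laboratory tests in 3.1.2. Weight has nothing comparable.

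**2. Who is affected.** SAP 2.5 gives 3 low-dose ambulatory, 16 high-dose ambulatory and 3 high-dose non-ambulatory participants: 3 + 16 + 3 = 22. Ambulatory participants number 3 + 16 = 19.

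**3. Illustration with height.** The starting sizes and gains here are assumptions, not trial data. Body mass index is weight in kg divided by height in metres squared. Suppose a boy weighs 25 kg at 122 cm, so his index is 25 / 1.22² = 16.8, and he gains 4 kg:

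| Height gain | Index afterwards | Change in index | SAP 6.1.7 shows |
|---|---|---|---|
| 0 cm | 29 / 1.22² = 19.5 | +2.7 | +4 kg |
| 2 cm | 29 / 1.24² = 18.9 | +2.1 | +4 kg |
| 4 cm | 29 / 1.26² = 18.3 | +1.5 | +4 kg |
| 6 cm | 29 / 1.28² = 17.7 | +0.9 | +4 kg |

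Now vary the assumed starting size as well. The largest change is at 20 kg and 112 cm with no height gain: 24 / 1.12² − 20 / 1.12² = +3.2. The smallest is at 35 kg and 138 cm with 6 cm of height gain: 39 / 1.44² − 35 / 1.38² = +0.4. The weight summary is +4 kg in every case.

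**4. Illustration without height.** Assume expected gain g of 2 to 5 kg per year, depending on age. Departure from expectation is observed change minus g.

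- Observed +3 kg: 3 − 5 = −2 kg if g is 5, 3 − 3 = 0 if g is 3, and 3 − 2 = +1 kg if g is 2.
- A boy 2 kg below expectation shows g − 2, which is 0 to +3 kg. A boy 2 kg above shows g + 2, which is +4 to +7 kg. Each range overlaps the expected range of +2 to +5 kg.
- Over 5 years, taking growth as linear, expected gain is 5 × 2 = 10 kg to 5 × 5 = 25 kg.

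**5. What standardising does.** In its simplest form, z = (observed − reference median for age) / reference SD for age. A boy who keeps his place in the reference distribution has a change in z of zero at any age. Excess gain makes the change positive and poor gain makes it negative. Expected growth is removed, and raw kilograms cannot do that.

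**The case against.** The best reply is that little would be missed in practice. SAP 6.1 says the Section 3.1 endpoints, weight among them, will be listed as well as summarised, and 22 participants can be read one by one. Continuous summaries include the minimum and maximum (SAP 5.2.1), so weight loss or an extreme gain would show. Untoward examination findings that meet the definition become adverse events (Protocol 9.2), and so do abnormal findings that the investigator considers adverse events (Protocol 8.2.2). These points stand. A reader might infer that the endpoint cannot detect any abnormal change, and the documents do not support that. What remains is that none of these routes has a criterion for weight, and none accounts for age.

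Height is in no endpoint list, and both documents allow the SAP to modify the outlined analyses. So the omission is an unexplained departure from Protocol 9.2. It is not the loss of a primary endpoint.

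Two further inferences are tempting and unsupported. One is that age confounds a comparison of cohorts on weight. SAP 5.1 plans no formal hypothesis testing, 6.1.7 is descriptive, and nothing shows that the cohorts differ in age. The other is that growth suppression is a documented expected harm. Protocol 1.2.1 names weight gain and hypothalamic-pituitary-adrenal effects, and does not name growth suppression.

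Finally, child growth standards may not fit the three non-ambulatory participants, who have no age limit at entry, and z-scores would not separate the product's effect from that of the glucocorticoids. Both limits are real. The first shapes the fix; the second applies equally to raw kilograms.

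**Conclusion.** The point holds in limited form. The raw kilogram summary in SAP 6.1.7 cannot distinguish excess or poor gain from expected growth in a group that is mostly 4 to 12 years old at entry and has no control. The SAP also omits, without explanation, the post-baseline height summary that Protocol 9.2 sets out. Gross changes would still be visible in listings, extremes and adverse event reports.

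The textual part needs no assumption beyond reading the visible SAP, parts of which are redacted. The size is illustrative only: an identical +4 kg spans about +0.4 to +3.2 in body mass index under the assumed sizes, and the 2 to 5 kg per year is likewise assumed. The conclusion needs only that expected gain is positive and varies with age.

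No enrolment halt criterion in Protocol 3.5 refers to weight. This should be corrected before the analysis, but it does not threaten the conduct of the trial.

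**What to change.** In SAP 6.1.7:

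- Restore post-baseline height, to match Protocol 9.2.
- Add change from baseline in weight-for-age, height-for-age and body-mass-index-for-age z-scores, by visit, dose cohort and ambulatory status.
- Name one growth reference. Protocol Appendix 1 already used growth charts specific to boys with this disease for its sirolimus simulations. A general reference and a disease-specific one answer different questions, so the choice must be stated.
- Report n (%) of participants whose z-score change crosses a threshold in either direction. Because the study is open-label, fix the threshold before the analysis and on grounds outside the trial's own data.
- Add individual plots for the two groups of three.
- Keep the raw kilogram summaries and listings.
- For non-ambulatory participants, footnote heights estimated from ulnar length, and report raw values only where age is beyond the reference range.

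The cost is SAP wording and derived variables. Age, height and weight are already collected, so there is no added burden on participants. The approach agrees with SAP 6.1.2, which already normalises laboratory values to paediatric ranges when normal ranges differ over time or between participants.
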